Each of the two population cohorts (South Asian and White British) has four sub-groups (clinically uninfected subjects, asymptomatic/mild, symptomatic moderate/severe, and recovered). After patient information sheets and consent, then oral health questionnaires (5mins), SWMF samples (5-15 mins), oral health (periodontal) examination (10 mins), and blood via venesection (5 mins). Patients will chew on a pellet of wax until approximately 4ml SWMF is recovered by drooling into sterile universal containers (between 5 and 10 minutes normally) after which the chewed wax will be wrapped in gauze and disposed with other clinical waste in adherence to infection control procedures. Blood samples may be taken before, during or after the SWMF collection. Repeat blood and stimulated SWMF will be taken at approximately 2 weeks, 4 weeks and 12 weeks after baseline for those participants willing to take part in the sequential studies. Oral examination and partial mouth recording will not be repeated unless any material change in oral condition is evident.

Uninfected subjects will be further defined as those who do not show antibodies to nuclear capsid protein antigens. The presence of such antibodies would indicate exposure to SARS-CoV2 rather than immunisation, and would be classified as asymptomatic if no history of symptoms.

Number of samples: With South Asian and White British participants, there will be up to 100 patient samples in each of the four sub-groups (uninfected subjects, asymptomatic/mild and moderate/severe disease, and recovered.). All will be assayed for immunological parameters, and the first 50 in each group for microbiome analysis, with the remainder stored for future analysis. The first 50 participants in each group will be invited to provide sequential samples.

Times of samples: There will be repeat samples of SWMF and blood at approximately 2, 4 and 12 weeks. Those SWMF at 4 weeks will be analysed for the microbiome in addition to the immunology (see table 1).

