Choice of time points: Mucosal immunological responses have a different and often shorter time frames than systemic responses. The 2 week post infection or post vaccination time point as well as the 4 week time point is to determine whether a response has been generated, and indicate possible kinetics of the mucosal response in comparison with systemic (serum) responses. The 12-week sampling point was selected as optimal to indicate longevity of any mucosal response, and any differential between a possible protective response of longer duration from a response of shorter duration.

Handling of samples: After collection, samples for GSTT haematology (Viapath) and blood glucose (if results not already available) will be sent to GSTT haematology. Study pseudoanonymised samples will be transported to the Centre for Host-Microbiome Interactions (CHMI) laboratories in Guy's Tower by the clinical research dentist. SWMF will be transported on ice. All samples will be subject to current infection control measures and containers pre-labelled. In the lab, SWMF samples will be centrifuged and immune factors including cytokines and anti-SARS-CoV2 antibodies assayed in the supernatant, whilst cellular factors determined in reconstituted pellet. DNA extraction for the microbiome studies will be performed on the saliva pellet. Peripheral blood T cell phenotypes will be assayed in the supernatant from plasma. Recruitment: Patients identified by the clinical team will be recruited by a clinical research assistant and consented. Uninfected subjects and ambulant patients will be recruited within Guys

and St Thomas' Hospital sites, from KCL sites and for General Medical Practice PIC (participant identification centre) sites. Symptomatic patients will be recruited from within outpatients or on the wards. From each subject, basic medical data will be collected and an oral health questionnaire applied, followed by SWMF, an oral examination and blood samples as above.

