The gene richness analysis will be done based on the updated count matrix to obtain the diversity of the samples at the gene level. A Wilcoxon test follow by Benjamini-Hochberg multiple testing correction will be used to obtain the significant changes between the cohorts. Next, we will map each sample to our already generated 1,942 oral Metagenomic Species Pangenomes (MSP), as an updated format for the metagenome species. The relative abundance of an MSP will be calculated using the mean abundance of its 100 ‘marker’ genes. To contrast the species abundance in different cohorts, we will perform Benjamini-Hochberg multiple testing correction of a Wilcoxon test. Functional analysis will also be performed using the PFAM and KEGG databases. Antimicrobial resistance analysis will be performed by searching reads using the CARD (Comprehensive Antimicrobial Resistance Database) database. In addition, “ortotyping” will be performed using the microbial information on the genus-level abundance with a Hellinger transformation with a Dirichlet multinomial mixtures (DMM) approach to cluster individual samples to distinct groups based on their microbiome composition, and a Fisher’s exact test will be used to identify the prevalent ortotype.

3. Sample Size, Selection and Withdrawal of Subjects

The success of the national vaccination programme has necessitated casting the recruitment net more widely than originally anticipated. Sample size is discussed in 2.4

Uninfected (vaccinated or unvaccinated) will be identified by advertising within KCL and GSTT sites, and at PIC sites, via social media and by recruitment at vaccination centres at GSTT or

testing centres at KCL/GSTT. Patients admitted to wards for non-COVID reasons and found to be SARS-CoV2 negative will be invited to participate. Uninfected (vaccinated) will be identified by recruitment at vaccination centres and by advertising within KCL and GSTT and PIC sites. Uninfected participants will be further defined as those who do not show antibodies to nuclear capsid protein antigens. The presence of such antibodies would indicate exposure to SARS-CoV2 rather than immunisation, and would be classified as asymptomatic if no history of symptoms.

All will be given the Patient Information Leaflet (PIL) about the study and access to the study website (<https://www.kcl.ac.uk/research/mimsa>)

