Asymptomatic/mild subjects will be recruited from those identified as positive for SARS-CoV2 carriage in routine testing at KCL or GSTT. In both cases local staff will inform them about the trial and give out a patient information sheet. A medical history will be taken from those who consent to take part in the research

Symptomatic moderate/severe patients will be recruited within Guys and St Thomas Hospital, mainly in conjunction with the GSTT COVID infection teams. Patients will be recruited from those admitted or planned to be admitted to GSTT with a recent onset (≤ 21 days) of symptoms of COVID-19 and a confirmed positive nasal/nasopharyngeal PCR test for SARS-CoV-2. They will be identified and approached by the clinical staff caring for them on the wards who will discuss the trial in outline and offer the PIL. Should the patient wish to consider participation after reading the PIL, the clinical research dentist (summoned by clinical ward staff) will obtain signatures of consent.

Recovered participants will be patients who have had COVID and fulfil the inclusion criteria. They will have either been discharged from GSTT or be attending either the post-COVID or ICU follow-up outpatient clinics and will be sent letters of invitation to participate. They will also be recruited from participating GP PIC sites, KCL sites and GSTT sites

Number of subjects	Subject selection
Group 1. SA1, BW1 Uninfected Subjects (n=100 each)	Uninfected subjects, both South Asian and White British will be recruited by advertisement within KCL or social media, from non-COVID in-patients or outpatients or attending A&E at GSTT and at SARS-CoV2 antigen testing centres and vaccination centres and at PIC sites. They will be furnished with the participant information leaflet and invited to take part in the study. After obtaining informed consent, oral examination, oral & general health questionnaires and samples of blood and stimulated whole mouth fluid (SWMF) (see below) will be taken either on the wards (inpatients), A&E or at the department of Oral Medicine at Guys Hospital
Group SA1v, BW1v (n=50)	In a subset of uninfected subjects from those attending for vaccination or volunteers, blood and SWMF will be taken 2 weeks after the first vaccination and 2 weeks after the second vaccination for immunology and microbiome analysis.

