3.1 Inclusion Criteria

Inclusion criteria
	
 • South Asian and White British persons and those diagnosed with symptomatic or asymptomatic COVID-19 infection, or recovered from COVID infection or previously uninfected. • Aged 18 or over. Able to understand and consent. • For inpatient groups: Confirmed COVID-19 positivity, symptoms and symptom onset within the past 21 days; Be recently (within 7 days) hospitalised with COVID-19 disease; Have COVID-19 disease proven by PCR testing for SARS-CoV-2 within the last 21 days; • Uninfected subjects: no history of COVID-19; not vaccinated; (negative for anti-SARS-CoV2 nucleoprotein antibodies at lab)
---------------------------	--

	
 • Recovered groups: Have had COVID-19 disease proven by PCR testing for SARS-CoV-2. • Those willing to participate on a single occasion but unwilling to participate with longitudinal samples will not be excluded. • Smoking, obesity, diabetes, heart disease, antibiotics or treatment related to COVID is not excluded.
--	--

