5.5 Data Recording/Reporting

The data obtained during this study will comply with community standards for research data. King's College London aspires to ISO 27001 standards for data security. All hard copy data and link codes will be kept in a GSTT locked and secure filing cabinet in a locked room based in the PI's office Department of Periodontology, Faculty of Dentistry, Oral and Craniofacial Sciences in Guys Dental Hospital. Additional back up of link codes will be stored on secure GSTT storage. All pseudoanonymised electronic data will be held on KCL firewalled computers, subject to KCL standard audits. In addition, data will be stored at KCL high performance computers with weekly backup program. Data will be recorded by a dedicated technician who will be HTA trained.

Data analyses:

The immunological markers will be compared between the healthy controls, asymptomatic and symptomatic COVID-19 patients using Mean, Median and non-parametric tests like Anova and Mann-Whitney rank sum tests. The immunological markers in the blood and SWMF will be compared and analysed at various time points of the disease progression. The key immunological parameters will be compared with the oral microbiome data to identify key biomarkers that may be indicative of the pathogenesis of the disease. These parameters will also be compared between the South Asian and the British-Caucasian population recruited in the UK. At the conclusion of the study, all the above analyses of the immunological and oral microbiome parameters will be compared among the age-matched and disease-matched participants in the UK and a collaborative, parallel study performed by collaborators in Chennai, India.

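### Section 5.5 calls the reference group 'healthy controls', but Group 1 also takes non-COVID hospital patients, and nothing balances recruitment source between SA1 and WB1

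*Protocol*

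**What the plan says.** **Analysis.** Protocol section 5.5 (Data analyses) states: "The immunological markers will be compared between the healthy controls, asymptomatic and symptomatic COVID-19 patients". The group tests named in 2.4 and 5.5 are rank tests without covariates: Mann-Whitney, Kruskal-Wallis with Dunn, and Wilcoxon with Benjamini-Hochberg correction for the microbiome.

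**Recruitment.** Section 3 describes Group 1 (SA1 and its White British counterpart, called WB1 in Table 1). One route is the community: "Uninfected (vaccinated or unvaccinated) will be identified by advertising within KCL and GSTT sites, and at PIC sites, via social media", together with testing and vaccination centres. Another is the hospital: "Patients admitted to wards for non-COVID reasons and found to be SARS-CoV2 negative will be invited to participate". The Group 1 row of the table in section 3 adds "from non-COVID in-patients or outpatients or attending A&E at GSTT" and provides for sampling on the wards or in A&E.

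**Eligibility.** Section 3.1 defines the group by COVID history, vaccination and serology: "Uninfected subjects: no history of COVID-19; not vaccinated; (negative for anti-SARS-CoV2 nucleoprotein antibodies at lab". For all groups it adds: "Smoking, obesity, diabetes, heart disease, antibiotics or treatment related to COVID is not excluded". Section 3.2 excludes malignancy, pregnancy and long-term immune suppression, but not other acute or chronic illness.

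**Section 2.2** uses the term "clinically uninfected subjects" and, on recruitment, says "Uninfected subjects and ambulant patients will be recruited within Guys" and St Thomas' sites, KCL sites and general-practice PIC sites. It does not mention in-patients or A&E for this group.

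**The concern.** The protocol has no group selected for health. Section 5.5 must therefore mean Group 1, and Group 1 is defined by absence of SARS-CoV2 infection. A person admitted for another illness and taking antibiotics can enter it and be reported as a healthy control.

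Two results are exposed:

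- **COVID v control.** The reference level depends on how many Group 1 participants came from hospital and on what their illness does to each marker.
- **South Asian v White British.** This is part of the primary endpoint in 2.1. Nothing in the protocol sets a quota, matching or stratification by source for SA1 against WB1. Matching is named only for the UK-India comparison in 5.5. If the source mix differs between the two groups, the recruitment difference appears in the test as a baseline ethnic difference in mucosal immunity or microbiome.

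The CRF contents listed in section 10 include medical history and current medication, but no field for recruitment source.

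**Working it through.** **1. The plan's own figure.** Section 2.4 asks for 30 to 50 values per parameter (more than 21 for immunology, more than 30 for microbiome). It gives no effect size, SD, significance level or power, so the figure cannot be reproduced. Back-solving d = √(2/n) × (1.96 + 0.84), that is, assuming two-sided 5% and 80% power, gives these detectable differences:

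| n per group | d (SD) |
|---|---|
| 21 | 0.87 |
| 30 | 0.72 |
| 50 | 0.56 |
| 100 | 0.40 |

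The point does not depend on these values. They show that effects of about half an SD are within the range the study could detect.

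**2. False ethnic difference, SA1 v WB1.** From the protocol: 50 to 100 per group (2.4), and the first 50 per group for microbiome (2.2). Assumed: hospital shares p₁ and p₂, hospital effect s in SD units, no true ethnic difference, one marker, two-sided 5%.

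- Spurious mean difference: Δ = (p₁ − p₂) × s
- Standard error: SE = √{[2 + s²(p₁(1−p₁) + p₂(1−p₂))]/n}
- Mann-Whitney signal: λ = (Δ/SE) × √(3/π), where √(3/π) = 0.977
- Rejection rate: P(Z > 1.96 − λ) + P(Z < −1.96 − λ)

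For 40% v 10%, p₁(1−p₁) + p₂(1−p₂) = 0.24 + 0.09 = 0.33:

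| n | s | Δ | SE | λ | Formula | Simulated |
|---|---|---|---|---|---|---|
| 100 | 0.5 | 0.15 | √(2.0825/100) = 0.144 | 1.02 | 17% | 17-18% |
| 100 | 1.0 | 0.30 | √(2.33/100) = 0.153 | 1.92 | 48% | 47-48% |
| 50 | 0.5 | 0.15 | 0.204 | 0.72 | 11% | 11% |
| 50 | 1.0 | 0.30 | 0.216 | 1.36 | 27% | 26-27% |

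The simulations used 4,000 runs per setting.

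A milder imbalance of 30% v 20% at 100 per group gives λ = 0.34 and 0.64, that is, about 6% and 10%. With equal shares (30% each), simulated rejection is 4.3-5.2%, so the nominal level is kept.

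**3. COVID v control.** Assumed: true COVID shift 0.5 SD, 100 per group, 40% of controls from hospital with effect s, and no such illness among the COVID group. The expected contrast is 0.5 − 0.4s.

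| s | Expected contrast | Simulated power |
|---|---|---|
| no hospital controls | 0.5 | 93% |
| +0.5 | 0.3 | 51% |
| +1.0 | 0.1 | 11% |
| −0.5 | 0.7 | above 99% |

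In the last row the extra power is not a gain, because the contrast is overstated by 0.2 SD. If the COVID group has the same 40% share of other illness, the expected contrast returns to 0.5 and power is 87-92%. The direction and size of the bias are therefore not determined by the protocol.

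**The case against.** The strongest reply is that this is one loose word. The synopsis, Table 1, section 3 and 3.1 all say uninfected, and 5.5 uses 'healthy controls' once without defining it. Both ethnic groups draw on the same list of sources, and the unequal shares above are invented. Medical history and medication are on the CRF, 2.4 mentions regression with clinical features, and an SAP that is not shown may add adjustment.

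Much of this stands. The rest of the protocol is consistent about who Group 1 is, and an imbalance is possible, not demonstrated. What remains is that the protocol fixes the recruitment sources, names unadjusted group tests and lists no CRF field for source. A later SAP could stratify by source only by reconstructing it from other records.

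Three stronger readings are tempting, and the documents do not support them:

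- **That hospital patients fill Group 1, or are acutely ill.** Community sources are listed alongside, no shares are given, and the text says only that patients were admitted for non-COVID reasons or attended A&E or outpatients. The support is in section 3; section 2.2 does not mention in-patients or A&E for this group.
- **That hospital controls dilute the COVID contrast.** That holds only if other illness moves a marker in the same direction as COVID. Group 2 also takes in-patients admitted for non-COVID reasons and A&E attenders, so hospital controls may be the closer comparator for those patients.
- **That a false ethnic difference will occur.** It needs a difference between SA1 and WB1 in the share or type of hospital recruits.

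**Conclusion.** The concern holds in a limited form. The label in 5.5 contradicts the recruitment in section 3 and the eligibility in 3.1 and 3.2. As written, the plan permits two biases: one of unknown direction in the COVID contrasts, and a false SA1 v WB1 difference if source mix differs. Under an assumed 40% v 10% split, the false-positive rate per marker is about 11% to 27% at 50 per group and 17% to 48% at 100, for hospital effects of 0.5 to 1.0 SD. It is near 5% when shares are equal and 6% to 10% for a mild imbalance at 100 per group. These rates also assume normal markers and an uncorrected 5% test; correction for multiple testing would change them. The bias does not shrink as the groups grow; larger groups only make it more likely to reach significance. The change is worth making because it is cheap during recruitment and hard to recover afterwards.

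**What to change.** 1. In 5.5, replace 'healthy controls' with 'uninfected controls'. A separate healthy subgroup defined by source would not deserve the name either, because 3.1 allows diabetes, heart disease and antibiotics whatever the source.
2. Add recruitment source to the CRF for all groups: in-patient, A&E, outpatient, or community (advertisement, testing or vaccination centre, PIC site). Every source listed for Group 1 then has a category.
3. Run SA1 v WB1, and uninfected v COVID, as rank tests stratified by hospital v community source (van Elteren's form of the Wilcoxon test), for immunology and microbiome alike. Stratify instead of splitting Group 1 into separate groups: halving a group of 50 leaves 25, below the more than 30 that 2.4 asks for microbiome samples.
4. Add a community-only sensitivity analysis where both groups have community recruits.
5. Reconcile Group 1's COVID-negative in-patients with the 3.1 criterion that inpatient groups have confirmed COVID positivity.

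**Cost.** One CRF field, some analysis wording, and a loss of precision where source is strongly unbalanced. If nearly all of Group 3 comes from hospital, community controls add little to that stratified contrast, and the pooled comparison should be shown beside it as descriptive. Stratifying removes the effect of source mix, but not differences in type of illness within hospital recruits. Medical history and medication on the CRF can help there.

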3.1 Inclusion Criteria

Inclusion criteria
	
 • South Asian and White British persons and those diagnosed with symptomatic or asymptomatic COVID-19 infection, or recovered from COVID infection or previously uninfected. • Aged 18 or over. Able to understand and consent. • For inpatient groups: Confirmed COVID-19 positivity, symptoms and symptom onset within the past 21 days; Be recently (within 7 days) hospitalised with COVID-19 disease; Have COVID-19 disease proven by PCR testing for SARS-CoV-2 within the last 21 days; • Uninfected subjects: no history of COVID-19; not vaccinated; (negative for anti-SARS-CoV2 nucleoprotein antibodies at lab)
---------------------------	--

	
 • Recovered groups: Have had COVID-19 disease proven by PCR testing for SARS-CoV-2. • Those willing to participate on a single occasion but unwilling to participate with longitudinal samples will not be excluded. • Smoking, obesity, diabetes, heart disease, antibiotics or treatment related to COVID is not excluded.
--	--

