2.3 Trial Flowchart

[figure not shown]

Table 1 Summary of Groups, Recruitment numbers, screening and sample collection

Patient Categories and timelines

		Baseline Im+Mb	10-14d	4 weeks	12 weeks*
South Asian	SA1 Uninfected	100	-	Im+Mb*	
	SA2 Asymptomatic/mild	100	Im	Im+Mb	Im
	SA3 Moderate/severe	100	Im	Im+Mb	Im
	SA4 Recovered	100		Im+Mb	Im+Mb
White British	WB1 Uninfected	100	-	Im+Mb*	
	WB2 Asymptomatic/mild	100	Im	Im+Mb	Im
	WB3 Moderate/Severe	100	Im	Im+Mb	Im
	WB4 Recovered	100		Im+Mb	Im+Mb
TOTAL	Participants	800	200	400	300
	Immunology samples	800	200	400	300
	Microbiome samples	800	-	400	100
	Blood samples	800	-	400	300

Samples for immunology studies (blood and stimulated whole mouth fluid- (SWMF) and microbiome (SWMF) are taken from all participants at baseline. Sequential samples of SWMF for immunology will be taken at approximately 2, 4 and 12 weeks in the first 50 of the COVID positive groups. Sequential samples for microbiome analysis will be performed on these samples at 4 weeks, and at 12 weeks in the recovered groups. The aim (following statistical advice) is to sample a minimum of 50 participants per group in the cross sectional part of the study, and a minimum of 30 per group in the sequential part.

* Post vaccination sample for subset of 50 two weeks after first and second vaccination.

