4.4 Schedule of Treatment for each visit

Please see section 2.2 trial design. There is no treatment involved in this study.

Patients having been identified by the clinical treatment team as being suitable for recruitment to the study, will be asked whether they would like to participate in the study and given a participant information sheet (PIS) by the clinical team providing their care. The patient will be given at least 30 minutes to read and decide whether they would like to proceed to attend the pre-sampling visit. Patients who do not wish to participate will receive standard clinical care as normal. Volunteers also will be provided the PIS and have at least 30 mins to read through before providing informed consent.

After the patient information sheet has been given and consent obtained, the medical and oral health questionnaires will be asked, followed by the collection of SWMF (5-15 mins). Patients will chew on a pellet of wax until approximately 4ml SWMF is recovered by drooling into sterile universal containers (normally 5-10 minutes). The chewed wax will be wrapped in gauze and disposed with other clinical waste in adherence to infection control procedures. The oral health examination (10 minutes) will take place. Blood samples total 15ml (approximately 5 minutes) may be taken before, during or after the SWMF collection. Ward visits and follow up visits of patients previously seen at GSTT will be recorded in patients' hospital notes using EPR. For volunteer ambulant participants not previously patients of GSTT, appointments will be made at Guys Dental Hospital and patients pre-registered. Visits will be recorded on EPR and SALUD. Each participant in the three infected sub-groups (mild, moderate, recovered) once enrolled in the study, and willing to participate in the sequential part, would have a total participation time of approximately 85 minutes and four visits over 12 weeks. Uninfected subjects would be either a single visit of 40 mins or 60 minutes with a follow-up visit at four weeks (but not including travelling time)

Oral Health Clinical Assessment

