5.1 Central/Local Laboratories

Blood samples designated for routine blood tests and glucose will be sent to the hospital blood pathology lab for processing and analysis according to routine processes.

The remaining blood samples will be processed and prepared in the Centre for Host Microbiome laboratory on [name], Guy’s Hospital. Microbial DNA extraction will be performed in these laboratories. Extracted microbial DNA identified by study number only will be sequenced by specialised commercial companies or academic institutions in the UK or non UK.

The salivary microbiome will be analysed on 50-100 patients per group after microbial DNA extraction with standardised protocol, using shotgun metagenomic sequencing on an Illumina NovoSeq generating > 20 million reads/sample. Sequencing will be performed by a commercial provider. Analysis of the sequencing data will be performed at KCL under the supervision of CHMI academics as described in section 2.4. The salivary metabolome will be determined using NMR. The longitudinal immune response and shifts in the oral microbiota will be correlated with COVID-19 severity as well as both COVID-19 and non-COVID-19 oral disease. We will identify significant differences in oral microbiota & immune responses during transition from viral to immunological to post-COVID-19 phases, identifying specific host factors as therapeutic targets.

Salivary secretory IgA antibody assay to study mucosal responses to antigens associated with COVID-19.

SARS is a closely related virus to SARS-CoV2. Several crystal structures have been published that describe how different antigens recognize the SARS spike protein receptor binding domain. These highlighted antigenic regions in the SARS spike protein. Structures are also now available for the homologous SARS-CoV2 spike protein receptor binding domain. The amino acid sequence of the spike protein from SARS & SARS-CoV2 were compared. Major differences were identified and 10 peptides constructed. Three of these have been selected and will be assayed by ELISA along with Capsid antigens obtained commercially. The group has extensive experience with ELISA techniques, and has performed preliminary experiments to verify their use in SWMF. (This kit has been developed and validated in King's College London, and methodology shared with VHS, Chennai for sample testing.)

Blood and SWMF lymphocyte phenotyping

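### The uninfected groups are unvaccinated in section 3.1 but vaccinated or unvaccinated in section 3, and vaccination is not an explicit CRF item, so spike-peptide antibody contrasts can be confounded

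*Protocol*

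**What the plan says.** **Eligibility.** Section 3.1 sets the rule for the uninfected groups (SA1 and WB1, the latter written BW1 in the section 3 table): "Uninfected subjects: no history of COVID-19; not vaccinated; (negative for anti-SARS-CoV2 nucleoprotein antibodies at lab").

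**Recruitment.** Section 3 says "Uninfected (vaccinated or unvaccinated) will be identified by advertising within KCL and GSTT sites" and, a few lines later, "Uninfected (vaccinated) will be identified by recruitment at vaccination centres and by advertising within KCL and GSTT and PIC sites".

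**Laboratory check.** Uninfected status is confirmed by absence of antibody to capsid protein. Of these antibodies, section 3 says: "The presence of such antibodies would indicate exposure to SARS-CoV2 rather than immunisation".

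**Assay.** Section 5.1 describes ten peptides built from differences between the SARS and SARS-CoV2 spike sequences, and continues: "Three of these have been selected and will be assayed by ELISA along with Capsid antigens obtained commercially". Responses to SARS-CoV2 antigens are one of the three components of the primary objective in section 2.1, beside innate immunity and the oral microbiome.

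**Post-vaccination subset.** The section 3 table adds groups SA1v and BW1v (n=50), from whom "blood and SWMF will be taken 2 weeks after the first vaccination and 2 weeks after the second vaccination". The Table 1 footnote reads "Post vaccination sample for subset of 50 two weeks after first and second vaccination".

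**Analysis and data capture.** Section 5.5 compares immune markers between healthy controls and the asymptomatic and symptomatic groups, and between the two populations, with non-parametric tests including Mann-Whitney. Section 2.4 adds Spearman, Kruskal-Wallis and logistic models. Neither names vaccination as a stratum or covariate. The CRF list in section 10 has a general line for medical history and medication but none for vaccination.

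**The concern.** A vaccinated person with no history of COVID-19 and no capsid antibody is eligible under section 3 and ineligible under 3.1. The reference group can therefore differ according to which page recruiting staff follow.

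This matters because vaccination is expected to act on the outcome. Section 2.2 uses the post-vaccination time point to see whether a response has been generated, and section 3 relies on capsid antibody because it marks infection and not immunisation. Antibody to spike-derived peptides has no such protection.

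If vaccinated share differs between two groups, part of any difference in spike-peptide antibody may come from vaccination and not from infection, severity or ethnicity. If vaccination is not recorded for each participant, later analysis cannot separate them.

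**Working it through.** **1. The passages side by side**

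| Item | Where | Content |
|---|---|---|
| Uninfected, eligibility | 3.1 | Unvaccinated only |
| Uninfected, recruitment | 3 | Either status; vaccinated people also sought separately |
| Laboratory check | 2.2, 3, 3.1 | Capsid antibody; does not detect vaccination |
| Infected and recovered | 3, 3.1 | No vaccination criterion |
| CRF list | 10 | No explicit vaccination item |
| Stated tests | 2.4, 5.5 | No vaccination stratum or covariate |

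Reading 3.1 as status at baseline, before a later dose, does not remove the conflict, because section 3 recruits people described as already vaccinated. Both readings leave a problem. Unvaccinated controls would be compared with infected groups of unrestricted status; mixed controls would bring an uncontrolled mix.

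**2. Size of the distortion (illustration)**

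The plan gives no figure on this point to reproduce. From section 2.4: 50 to 100 participants per group for the cross-sectional comparison. Assumed, because the documents give none: vaccination shifts spike-peptide antibody by D = 1, 2 or 3 within-stratum SDs; vaccinated shares p1 and p2; normal values; no true group difference.

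Spurious mean difference = D × (p2 − p1):
- 60 v 70%: 0.1 to 0.3 SD
- 50 v 70%: 0.2 to 0.6 SD
- 0 v 80%: 0.8 to 2.4 SD

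False-positive rate of an unadjusted two-sided 5% Mann-Whitney test, 4,000 simulated trials per cell, ranges over D = 1 to 3:

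| Vaccinated shares | n=50 per group | n=100 per group |
|---|---|---|
| Equal (0/0, 50/50, 80/80%) | 4.3-5.3% | 4.5-5.6% |
| 60 v 70% | 7-14% | 10-22% |
| 50 v 70% | 15-39% | 26-66% |
| 40 v 80% | 45-93% | 73-99.9% |
| 0 v 80% | 96-100% | 100% |

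With unequal shares the error grows with sample size, because the test is detecting a real difference in vaccination.

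**3. The choice of reference group changes the answer**

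Suppose infection truly adds 0.7 SD, D = 2, 80% of the infected group is vaccinated, and n=50 per group. Expected difference = 0.7 + 2 × (0.8 − share vaccinated among controls):
- controls 0% vaccinated: 0.7 + 1.6 = 2.3 SD; rejection 100%
- controls 80%: 0.7 + 0 = 0.7 SD; rejection 76%
- controls 100%: 0.7 − 0.4 = 0.3 SD; rejection 32%

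The bias can inflate or mask a true effect.

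**4. The uninfected 4-week samples**

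The Table 1 total of 400 at four weeks is 8 × 50, so it counts 2 × 50 = 100 uninfected participants; without them it is 6 × 50 = 300. The SA1 and WB1 cells at four weeks carry the asterisk of the post-vaccination footnote, but the 12-week column header carries one too. The footnote speaks of a subset of 50 without saying whether that is per population or in total. If in total, 100 − 50 = 50 of these samples are not post-vaccination. Section 4.4 says only: "Uninfected subjects would be either a single visit of 40 mins or 60 minutes with a follow-up visit at four weeks".

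**The case against.** **Bias is not automatic.** A reader might infer that the spike contrasts simply measure vaccine mix. They do not: with equal shares the test keeps its 5% level. If 3.1 governs, SA1 v WB1 compares two unvaccinated groups and is free of this problem. For other South Asian v White British contrasts the bias depends on uptake, which the documents do not give. This stands.

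**Vaccination is not ignored.** SA1v and BW1v are sampled after each dose for immunology and microbiome analysis, so it would be wrong to say that no analysis concerns vaccination. It is correct only that no listed method stratifies or adjusts for it.

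**Covariates belong in a SAP, and history may be captured anyway.** Covariate choice may indeed sit in a SAP that is not shown. The CRF medical-history line, or the medical data mentioned in section 2.2, could hold vaccination. But nothing requires it for every participant, and a SAP cannot adjust for data that were not collected.

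**Follow-up.** A reader might infer from Table 1 that every uninfected follow-up sample is post-vaccination, or that section 4.4 allows one visit where section 3 needs two. The asterisk and the subset of 50 are too ambiguous for the first, and 4.4 does not mention SA1v or BW1v. What remains is a need for clarification.

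**Number of targets.** The spike peptides cannot be expressed as a fraction of the antibody targets, since section 5.1 does not count the capsid antigens.

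**Scope.** Anti-spike response is one part of the primary objective; innate immunity and the microbiome are the others.

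**Conclusion.** The concern holds in this form. The definition of the uninfected groups contradicts itself in current text, the laboratory check cannot resolve it, and vaccination is not explicitly recorded. Contrasts in antibody to the three spike-derived peptides can be confounded to the extent that vaccinated share differs between groups. This is clearest for uninfected v infected or recovered, where the risk exists under either definition.

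The size is unknown from the documents. Under the assumed 1-3 SD shift it runs from modest (7-22% false positives at 60 v 70%, across both group sizes) to near certain (96-100% at 0 v 80%). Those figures show sensitivity and do not predict what this study will find. On the protocol's own reasoning, capsid-antibody contrasts are not distorted by vaccination in this way.

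**What to change.** 1. Reconcile section 3 with section 3.1 so that one statement of vaccination status defines SA1 and WB1. Which definition to adopt is for the investigators.
2. Add vaccination status, number of doses and date of last dose to the CRF for all groups.
3. Stratify or adjust every spike-antigen contrast by vaccination: status first, then doses and time since last dose as covariates where numbers allow.
4. State in Table 1, the section 3 table and section 4.4 which uninfected 4-week samples are post-vaccination, whether the subset is 50 in total or per population, and how many visits it has. Analyse those samples as a separate before/after comparison, not pooled with uninfected follow-up that had no intervening dose.
5. Do not substitute the capsid response as the infected v uninfected contrast. The uninfected are selected for lacking it, so a difference is built in.

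Cost: wording changes and three CRF fields, with no added participants for the recording itself; some loss of precision from adjustment in groups of 50-100; and, if the definition is settled as unvaccinated only, a smaller recruitment pool. Sections 2.2 and 3 already say that the vaccination programme reduced the patient pool and forced wider recruitment.
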